**Table 7: Dose Modifications for INCB024360 (Epacadostat)**

Current Dose	Dose Adjustment
300 mg BID	100 mg BID
100 mg BID	50 mg BID
50 mg BID	25 mg BID

A maximum of 2 dose reductions of INCB024360 are permitted. Twenty-five mg BID is the lowest dose of epacadostat in this Protocol. See the general instructions at the bottom of Table 8 for guidance regarding the re-occurrence of an AE when a subject has had his or her epacadostat dose reduced to 25 mg BID.

### 5.6.3. Procedures for Subjects Exhibiting Immune-Related Adverse Events

This section is meant to apply to suspected irAEs or events of clinical interest (ECIs) of a potential immunologic etiology from INCB024360, MK-3475 or the combination.

Events of clinical interest of a potential immunologic etiology or irAEs may be defined as an AE of unknown etiology, associated with drug exposure and consistent with an immune phenomenon. irAEs may be predicted based on the nature of the MK-3475 or INCB024360 compounds, their mechanism of action, and reported experience with immunotherapies that have a similar mechanism of action. Special attention should be paid to AEs that may be suggestive of potential irAEs. An irAE can occur shortly after the first dose or several months after the last dose of treatment. Of note, the requirement for reporting ECIs applies to all groups, including comparators, of MK-3475.

If an irAE is suspected, efforts should be made to rule out neoplastic, infectious, metabolic, toxin or other etiologic causes before labeling an AE as an irAE. Subjects who develop a  $\geq$  Grade 2 irAE should be discussed with the sponsor.

General recommendations to managing irAEs not detailed elsewhere in the Protocol are detailed in Table 8 and below.

**Table 8: Dose Modification and Toxicity Management Guidelines for Immune-Related Adverse Events**

Toxicity	Grade	Study Treatment	Action Taken	AE Management	Monitor, Follow-up and Restart Guidelines
Diarrhea/ Colitis	2-3	MK-3475	Withhold until toxicity resolves to Grade 0-1	Administer corticosteroids (initial dose of 1-2 mg/kg prednisone or equivalent) followed by taper	
 
Subjects should be carefully monitored for signs and symptoms of enterocolitis (such as diarrhea, abdominal pain, blood or mucus in stool, with or without fever) and of bowel perforation (such as peritoneal signs and ileus).
 
All subjects who experience diarrhea/colitis should be advised to drink liberal quantities of clear fluids. If sufficient oral fluid intake is not feasible, fluid and electrolytes should be substituted via IV infusion.
 
For Grade 2 or higher diarrhea, consider GI consultation and endoscopy to confirm or rule out colitis.
 
If toxicity does not resolve within 12 weeks of last dose, or cannot taper below 10 mg or less of prednisone or equivalent within 12 weeks, must permanently discontinue.
 
Restart INCB024360 at same dose if event assessed as unrelated, decrease by 1 dose level if assessed as related.
 

		INCB024360	Withhold until toxicity resolves to Grade 0-1		
	4 or recurrent Grade 3	MK-3475	Permanently discontinue	Administer corticosteroids (initial dose of 1-2 mg/kg prednisone or equivalent) followed by taper	
		INCB024360	Permanently discontinue		

**Table 8: Dose Modification and Toxicity Management Guidelines for Immune-Related Adverse Events (Continued)**

Toxicity	Grade	Study Treatment	Action Taken	AE Management	Monitor, Follow-up and Restart Guidelines
AST, ALT, or Increased Bilirubin	2	MK-3475	Withhold until toxicity resolves to Grade 0-1	Administer corticosteroids (initial dose of 0.5-1 mg/kg prednisone or equivalent) followed by taper	
 
Monitor with liver function tests (consider weekly or more frequently until liver enzyme values return to baseline or are stable.
 
If toxicity does not resolve within 12 weeks of last dose, or cannot taper below 10 mg or less of prednisone or equivalent within 12 weeks, must permanently discontinue.
 
Restart INCB024360 at same dose if event assessed as unrelated, decrease by 1 dose level if assessed as related.
 

		INCB024360	Withhold until toxicity resolves to Grade 0-1		
	3-4	MK-3475	Permanently discontinue	Administer corticosteroids (initial dose of 0.5-1 mg/kg prednisone or equivalent) followed by taper.	
		INCB024360	Permanently discontinue		
Type 1 diabetes mellitus (T1DM) (if new onset) or Hyperglycemia a	T1DM or 3-4 hyperglycemia associated with evidence of $\beta$ -cell failure	MK-3475	Withhold until toxicity resolves to Grade 0-1	Initiate insulin replacement therapy for subjects with T1DM Administer anti-hyperglycemic in subjects with hyperglycemia	
 
Monitor subjects for hyperglycemia or other signs and symptoms of diabetes.
 
Resume MK-3475 when subjects are clinically and metabolically stable.
 
Resume INCB024360 when subjects are clinically and metabolically stable.
 
Restart INCB024360 at same dose if event assessed as unrelated, decrease by 1 dose level if assessed as related.
 

		INCB024360	Withhold until toxicity resolves to Grade 0-1		

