#### 3.2. Subject Inclusion Criteria

The following criteria are required for inclusion in the study:

1. Male or female subjects, age 18 years or older on day of signing consent.
2. Willingness to provide written informed consent/assent for the study.
3. For Phase 1: Histologically or cytologically confirmed Stage IIIB, Stage IV, or recurrent NSCLC, melanoma, transitional cell carcinoma of the GU tract, clear cell RCC, TNBC, adenocarcinoma of the endometrium, or SCCHN.
4. For Phase 2: Histologically or cytologically confirmed melanoma, transitional cell carcinoma of the GU tract, SCCHN, ovarian cancer, TNBC, DLBCL, NSCLC, MSI high CRC, clear cell RCC, gastric cancer, and HCC.
5. Life expectancy > 12 weeks.
6. ECOG performance status 0 to 1.
7. Presence of measurable disease per RECIST v1.1 for solid tumors or the Lugano classification ([Cheson et al 2014](#)) for subjects with DLBCL.
8. Laboratory and medical history parameters within Protocol-defined range. NOTE: If the screening laboratory tests below were conducted > 7 days prior to treatment initiation, they will need to be repeated on Day 1 before initiation of treatment. Hematology and coagulation testing are central testing; therefore, central laboratory results should be used to determine eligibility for those relevant analytes below unless central laboratory results are not available at the time of enrollment or are not within the 7-day window before Cycle 1 Day 1. In this case, local laboratory results may be used to confirm eligibility. Chemistry testing is local testing; therefore, local results should be used for those relevant analytes below.
  - a. Absolute neutrophil count  $\geq 1.5 \times 10^9/L$  (for subjects with DLBCL, in no case  $< 1.0 \times 10^9/L$ ).
  - b. Platelets  $\geq 100 \times 10^9/L$  (for subjects with DLBCL or HCC in no case  $< 50 \times 10^9/L$ ).
  - c. Hemoglobin  $\geq 9$  g/dL or  $\geq 5.6$  mmol/L (transfusion is acceptable to meet this criterion).

- d. Serum creatinine  $\leq 1.5 \times$  institutional upper limit of normal (ULN) OR measured or calculated creatinine clearance (glomerular filtration rate can also be used in place of creatinine or CrCl)  $\geq 50$  mL/min for subjects with creatinine levels  $> 1.5 \times$  institutional ULN.
  - e. AST/ALT  $< 2.5 \times$  ULN OR  $\leq 5 \times$  ULN for subjects with liver metastases. For subjects with HCC: AST/ALT  $< 5 \times$  ULN. For other specific exceptions medical monitor approval is required.

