  - f. Total bilirubin  $\leq 1.5 \times$  ULN **OR** direct bilirubin  $\leq$  ULN for subjects with total bilirubin  $> 1.5 \times$  ULN.)
    - If there is no institutional normal range available for the direct bilirubin, the direct bilirubin should be  $< 40\%$  of the total bilirubin.
    - In no case can total bilirubin exceed  $3.0 \times$  ULN.
  - g. International normalized ratio (INR) or prothrombin time (PT)  $\leq 1.5 \times$  ULN unless subject is receiving anticoagulant therapy as long as PT or INR is within therapeutic range of intended use of anticoagulants. Subjects with HCC must have INR  $\leq 2.3$ .
  - h. Activated partial thromboplastin time (aPTT)  $\leq 1.5 \times$  ULN unless subject is receiving anticoagulant therapy, as long as PTT is within therapeutic range of intended use of anticoagulants
9. For Phase 1: Subjects who have advanced or metastatic disease as noted above who have received at least 1 prior therapy for their disease under study or have advanced or metastatic disease for which no curative treatment is available.
10. For Phase 2 expansion cohorts: Subjects with NSCLC, melanoma, transitional cell carcinoma of the GU tract, SCCHN, ovarian cancer, DLBCL, TNBC, MSI high CRC, clear cell RCC, gastric cancer, and HCC.
- a. Phase 2 expansion: NSCLC (PD-L1 positive and PD-L1 low/negative or indeterminate cohorts).
    - Subjects who have received at least 1 prior systemic chemotherapy regimen for Stage IIIB, Stage IV, or recurrent NSCLC (not including neoadjuvant and/or adjuvant therapy except as described below).
      - One prior systemic regimen must include a platinum-based therapy. Investigational agents used in combination with standard therapies are allowed. Subjects who have a non-platinum-based regimen may be enrolled with medical monitor approval.
    - Documentation of mutation status. Tumors with driver mutations (eg, epidermal growth factor receptor mutation positive or anaplastic lymphoma kinase fusion oncogene positive) treated with a targeted therapy are permitted; however, subjects should have progressed on or be intolerant to the targeted therapy.

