
General Instructions:
 
 
Corticosteroid taper should be initiated upon AE improving to Grade 1 or less and continue to taper over at least 4 weeks.
 
For situations where MK-3475 and INCB024360 have been withheld, MK-3475 and INCB024360 can be resumed after AE has been reduced to Grade 1 or 0, and corticosteroid has been tapered. MK-3475 and INCB024360 should be permanently discontinued if AE does not resolve within 12 weeks of last dose or corticosteroids cannot be reduced to <math>\leq 10</math> mg prednisone or equivalent per day within 12 weeks.
 
For severe and life-threatening irAEs, IV corticosteroid should be initiated first followed by oral steroid. Other immunosuppressive treatment should be initiated if irAEs cannot be controlled by corticosteroids.
 
If the same AE that required INCB024360 dose reductions to the 25 mg BID dose level re-occurs, regardless of the causality to INCB024360, INCB024360 should be discontinued. If a participant who is being treated at INCB024360 25 mg BID has a different AE that is considered unrelated to INCB024360 by the investigator, the participant may resume study treatment at 25 mg BID after discussion with the study medical monitor.
 
 
NOTES:
 
 
For participants with Grade 3 or 4 immune-related endocrinopathy where withholding of MK-3475 and INCB024360 is required, MK-3475 and INCB024360 may be resumed when AE resolves to <math>\leq</math> Grade 2 and is controlled with hormonal replacement therapy or achieved metabolic control (in case of T1DM)
 
Withhold OR permanently discontinue MK-3475 + INCB024360 at the discretion of the Investigator.
 
Participants with Grade 3 rash in the absence of desquamation, no mucosal involvement, does not require systemic steroids, and resolves to Grade 1 within 14 days does not have to hold study treatment.
 
 
Abbreviations: AEs = adverse events; ALT (SGPT) = alanine aminotransferase (serum glutamic pyruvic transaminase); AST (SGOT) = aspartate aminotransferase (serum glutamic oxaloacetic transaminase); CTCAE = Common Terminology Criteria for Adverse Events; IV = intravenous; irAE = immune-related adverse events; T1DM = Type 1 diabetes mellitus.
					

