APPENDIX B. LABORATORY GRADING

Laboratory	Grade 1	Grade 2	Grade 3	Grade 4
Haptoglobin decreased	< LLN	-	-	-
Hemoglobin decreased	< LLN - 100 g/L	< 100 - 80 g/L	< 80 g/L	-
Hemoglobin increased	Increase in > 0 - 2 gm/dL above ULN or above baseline if baseline is above ULN	Increase in > 2 - 4 gm/dL above ULN or above baseline if baseline is above ULN	Increase in > 4 gm/dL above ULN or above baseline if baseline is above ULN	-
Lymphocyte count decreased	$<$ LLN - 0.8 \times 10 ⁹ /L	$< 0.8 - 0.5 \times 10^{9}/L$	$< 0.5 - 0.2 \times 10^{9}/L$	$< 0.2 \times 10^{9}/L$
Lymphocyte count increased	_	$> 4000/\text{mm}^3 - 20,000/\text{mm}^3$	$> 20,000/mm^3$	-
Neutrophil count decreased	< LLN - 1.5 × 10 ⁹ /L	< 1.5 - 1.0 × 10 ⁹ /L	$< 1.0 - 0.5 \times 10^{9}/L$	$< 0.5 \times 10^{9}/L$
Platelet count decreased	$<$ LLN - 75.0 \times 10 ⁹ /L	$< 75.0 - 50.0 \times 10^{9}/L$	$< 50.0 - 25.0 \times 10^{9}/L$	$< 25.0 \times 10^{9}/L$
White blood cell decreased	$<$ LLN - 3.0 \times 10 ⁹ /L	$< 3.0 - 2.0 \times 10^{9}/L$	$< 2.0 - 1.0 \times 10^{9}/L$	$< 1.0 \times 10^{9}/L$
Activated partial thromboplastin time prolonged	> ULN - 1.5 × ULN	> 1.5 - 2.5 × ULN	> 2.5 × ULN	-
INR increased	> 1 - 1.5 × ULN	> 1.5 - 2.5 × ULN	$> 2.5 \times ULN$	-
Alanine aminotransferase increased	$>$ ULN - 3.0 \times ULN	> 3.0 - 5.0 × ULN	> 5.0 - 20.0 × ULN	> 20.0 × ULN
Alkaline phosphatase increased	> ULN - 2.5 × ULN	> 2.5 - 5.0 × ULN	> 5.0 - 20.0 × ULN	> 20.0 × ULN
Aspartate aminotransferase increased	$>$ ULN - 3.0 \times ULN	> 3.0 - 5.0 × ULN	> 5.0 - 20.0 × ULN	> 20.0 × ULN
Blood bilirubin increased	> ULN - 1.5 × ULN	> 1.5 - 3.0 × ULN	> 3.0 - 10.0 × ULN	> 10.0 × ULN
CD4 lymphocytes decreased	$<$ LLN - 0.5 \times 10 ⁹ /L	$< 0.5 - 0.2 \times 10^{9}/L$	< 0.2 - $0.05 \times 10^9/L$	$< 0.05 \times 10^{9}/L$
Cholesterol high	> ULN - 7.75 mmol/L	> 7.75 - 10.34 mmol/L	> 10.34 - 12.92 mmol/L	> 12.92 mmol/L
CPK increased	> ULN - 2.5 × ULN	> 2.5 - 5 × ULN	> 5 - 10 × ULN	$> 10 \times ULN$
Creatinine increased	> 1 - 1.5 × baseline; > ULN - 1.5 × ULN	> 1.5 - 3.0 × baseline; >1.5 - 3.0 × ULN	> 3.0 baseline; > 3.0 - 6.0 × ULN	> 6.0 × ULN
Fibrinogen decreased	< 1.0 - 0.75 × LLN or < 25% decrease from baseline	< 0.75 - 0.5 × LLN or 25 - < 50% decrease from baseline	< 0.5 - 0.25 × LLN or 50 - < 75% decrease from baseline	< 0.25 × LLN or 75% decrease from baseline or absolute value < 50 mg/dL
GGT increased	> ULN - 2.5 × ULN	> 2.5 - 5.0 × ULN	> 5.0 - 20.0 × ULN	> 20.0 × ULN

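### For non-HCC subjects admitted with Grade 2 liver tests, return to baseline after an immune-related hepatic hold fails the Table 8 restart condition, other Protocol rules differ, and none is said to govern

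*Protocol*

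**What the plan says.** **Entry.** Protocol Section 3.2, criterion 8e, sets a general AST/ALT limit below 2.5 x ULN but allows up to and including 5 x "ULN for subjects with liver metastases". Criterion 8f allows total bilirubin above 1.5 x ULN when direct bilirubin is within limits, subject to a ceiling ("In no case can total bilirubin exceed" 3.0 x ULN).

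**Grading.** SAP Appendix B, in the row "Alanine aminotransferase increased" and the matching AST row, puts Grade 2 at above 3.0 and up to 5.0 x ULN. For bilirubin, Grade 2 is above 1.5 and up to 3.0 x ULN.

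**Hold and restart.** For a Grade 2 hepatic event, Table 8 (Section 5.6.3) gives the same instruction for each drug: "Withhold until toxicity resolves to Grade 0-1". If the event has not resolved within 12 weeks of the last dose, discontinuation is permanent. General Instruction 2 under the table repeats the threshold: "MK-3475 and INCB024360 can be resumed after AE has been reduced to Grade 1 or 0, and corticosteroid has been tapered". The hepatic row mentions baseline only in its advice on how long to monitor liver tests ("until liver enzyme values return to baseline or are stable"), not as a restart condition.

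**The concern.** The trial deliberately admits some subjects whose liver tests are already Grade 2, and then states a restart condition below the level at which they were admitted. Other parts of the same Protocol use the subject's own baseline or allow continuation at Grade 2. Two clinicians relying on different passages could reach opposite decisions for the same laboratory course: one resumes treatment, the other ends it permanently.

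The choice also reaches the tables. The SAP summarizes duration of treatment (Section 6.4) and events leading to discontinuation of each drug (Section 8.2.2), so the same course could be reported in two ways. The laboratory summaries count only worsening of grade from baseline (Section 8.3.2). A rise within Grade 2 would therefore not count there, although under Table 8 it could end treatment.

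**Working it through.** The plan gives no figure for this point, so the check compares limits and then sets the rules side by side.

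**Step 1: overlap of the entry limits with Grade 2 (SAP Appendix B).**
- AST/ALT, liver metastases: entry up to 5.0 x ULN; Grade 2 is above 3.0 and up to 5.0. The whole Grade 2 range is admitted.
- AST/ALT, other non-HCC subjects: entry below 2.5 x ULN. No overlap.
- Total bilirubin: entry up to 3.0 x ULN through the direct-bilirubin alternative; Grade 2 is above 1.5 and up to 3.0. The whole Grade 2 range is admitted, by that route only.

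**Step 2: what triggers the hold.** Section 8.1.1 defines an adverse event as a new or worsened finding, so a stable Grade 2 baseline value is not one. A clinically meaningful worsening of a pre-existing abnormality can be. Section 5.6.3 then requires that the event be suspected as immune-related after efforts to exclude other causes.

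**Step 3: apply the Table 8 condition.** Let b be baseline and p the peak, in multiples of ULN.
- AST/ALT: 3.0 < b < p ≤ 5.0. Grade 1 ends at 3.0. On return to b, b > 3.0, so the condition is not met.
- Bilirubin: 1.5 < b < p ≤ 3.0. Grade 1 ends at 1.5. On return to b, b > 1.5, so the condition is not met.
- If p passes 5.0 (AST/ALT) or 3.0 (bilirubin), the event is Grade 3, for which Table 8 requires permanent discontinuation. The restart wording then plays no part.

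**Step 4: the competing rules for a subject who returns to a Grade 2 baseline.**

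| Rule | Reference for restart | Result |
|---|---|---|
| Table 8 hepatic row and General Instruction 2 | Grade 0 or 1 | Not met; permanent discontinuation at 12 weeks |
| Table 6, nonhematologic Grade 2 | Grade 1 or lower, or baseline | Met |
| Section 5.6.2, paragraph after Table 6 | Laboratory event still Grade 2 after 12 weeks, asymptomatic and controlled, investigator and sponsor agree | May continue |
| Appendix J (HCC only) | Baseline grade if Grade 2 at baseline (viral flare); baseline if abnormal at baseline (immune-related hepatitis) | Met, subject to its other conditions |

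**Step 5: look for a rule of precedence.** Table 6 and the paragraph after it both refer the reader to Section 5.6.3 for immune-related events. Section 5.6.3 describes Table 8 as covering such events where they are not detailed elsewhere in the Protocol. For HCC, Table 6 points to Appendix J. For non-HCC subjects, nothing states whether the baseline alternative in Table 6 or the agreement route in Section 5.6.2 survives once the event is called immune-related.

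**The case against.** The case against has four parts.

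- **A stricter restart threshold is not in itself an error.** Requiring Grade 0 or 1 after a suspected immune hepatic event may be a deliberate clinical choice. That stands, and is why this point takes no view on which rule is right. It does not explain why Table 6 and Section 5.6.2 say something different without an order of precedence.
- **There are central controls.** Section 5.6.2 requires discussion with the medical monitor before resuming after an interruption for liver test abnormalities, and Section 5.6.3 asks that immune-related events of Grade 2 or higher be discussed with the sponsor. This stands and limits variation between sites. The people consulted still face the same conflicting text.
- **The route is narrow.** It needs a non-HCC subject with a Grade 2 baseline, a worsening that stays within Grade 2, an immune attribution, and recovery only as far as baseline. This stands. Section 1.3.3 also suggests few cases: among 294 Phase 2 subjects, neither ALT nor AST increase is in the list of treatment-related events at 5% or more, and Grade 3/4 increases numbered 2 each. Those figures cover all entrants; rates in subjects admitted at Grade 2 are not given and could be higher.
- **Enrollment is closed.** Under Amendment 10, criteria 8e and 8f admit nobody further. This stands, but that amendment's stated purpose is to guide handling of subjects still on study, and Table 8 remains in force for them.

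A reader might infer that subjects admitted at Grade 2 can never restart after a hepatic hold. The documents do not support that: values can fall below baseline, Table 6 accepts baseline, and Section 5.6.2 has the agreement route. Nor are HCC subjects caught, because Appendix J provides for them.

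**Conclusion.** The inconsistency is real but limited. For non-HCC subjects with an admitted Grade 2 baseline and a suspected immune-related hepatic worsening within Grade 2, Table 8 read literally leads to permanent discontinuation despite recovery to baseline. Table 6 would allow restart, and Section 5.6.2 may allow continuation. The Protocol does not say which prevails.

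The documents give neither the share of subjects who entered at Grade 2 nor a hepatic immune-related event rate among them, so the number affected cannot be computed. It is probably small, and the point now bears only on subjects still on treatment. A reader might go further and infer reduced response rates in cohorts with liver disease; nothing in the documents gives a basis for that.

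The conclusion assumes that the SAP Appendix B ranges (CTCAE v4.03) are those used for dosing decisions. The Protocol cites CTCAE v4.0 and does not print the ranges.

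**What to change.** Reconcile inclusion criteria 8e and 8f, Table 6, the paragraph after Table 6 in Section 5.6.2, the Table 8 hepatic row and General Instruction 2. One stated rule should govern hold, restart and discontinuation for hepatic immune-related events in non-HCC subjects with a Grade 2 baseline, and the text should say how it relates to the other passages. Which rule that is, including whether it refers to absolute grade or to baseline, is for the clinical team.

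The cost is Protocol wording, or a written clarification to sites with subjects still on treatment. No sample size or analysis changes.

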**Table 8: Dose Modification and Toxicity Management Guidelines for Immune-Related Adverse Events (Continued)**

Toxicity	Grade	Study Treatment	Action Taken	AE Management	Monitor, Follow-up and Restart Guidelines
Hypophysitis	2	MK-3475	Withhold until toxicity resolves to Grade 0-1	Administer corticosteroids and initiate hormonal replacements as clinically indicated	
 
Monitor for signs and symptoms of hypophysitis (including hypopituitarism and adrenal insufficiency).
 
Restart INCB024360 at same dose if event assessed as unrelated, decrease by 1 dose level if assessed as related.
 
If toxicity does not resolve within 12 weeks of last dose, must permanently discontinue.
 

		INCB024360	Withhold until toxicity resolves to Grade 0-1		
	3-4	MK-3475	Withhold or permanently discontinue b	Administer corticosteroids and initiate hormonal replacements as clinically indicated	
 
Monitor for signs and symptoms of hypophysitis (including hypopituitarism and adrenal insufficiency).
 
Restart INCB024360 at same dose if event assessed as unrelated, decrease by 1 dose level if assessed as related
 
If toxicity does not resolve within 12 weeks of last dose, must permanently discontinue.
 

		INCB024360	Withhold or permanently discontinue b		
Hyperthyroidism a	2	MK-3475	Continue	Treat with non-selective beta-blockers (eg, propranolol) or thionamides as appropriate	
 
Monitor for signs and symptoms of thyroid disorders.
 
If toxicity does not resolve within 12 weeks of last dose, must permanently discontinue.
 

		INCB024360	Continue		
	3-4	MK-3475	Withhold or permanently discontinue b	Treat with non-selective beta-blockers (eg, propranolol) or thionamides as appropriate	
 
Monitor for signs and symptoms of thyroid disorders.
 

		INCB024360	Withhold or permanently discontinue b		
Hypothyroidism a	2-4	MK-3475	Continue	Initiate thyroid replacement hormones (eg, levothyroxine or liothyronine) per standard of care	
 
Monitor for signs and symptoms of thyroid disorders.
 
If toxicity does not resolve within 12 weeks of last dose, must permanently discontinue.
 

		INCB024360	Continue		

